8. AEs will be collected from the time of informed consent through 30 days following the last dose of study treatment or until initiation of a new anticancer treatment, whichever occurs first.
9. Brain scan and bone imaging will be performed at screening/baseline. Repeat at response assessment time points if metastases were identified at screening/baseline, or if metastasis is known or suspected, or as clinically indicated throughout the study.
10. Imaging/disease assessment will be performed at screening/baseline and every 8 weeks (56 days \pm 7 days) from the first dose of study treatment throughout the study. Baseline imaging performed prior to informed consent as part of standard of care may be used as long as it is performed within 28 days prior to the first dose of study treatment. * Inclusion of neck anatomy, chest, abdomen, pelvis is required at all imaging visits for the head and neck cancer cohort, cervical/cervicothoracic junction and esophagus malignancy cancer types. Additional neck anatomy imaging should be performed as clinically indicated for all other cohorts. If neck imaging is obtained at a post-baseline timepoint, then it should be submitted at every timepoint thereafter. Copies of all imaging scans will also be sent to the independent review facility in a timely manner.
11. If disease response is assessed as complete response or partial response by investigator, a confirmatory imaging scan is required 4 weeks (28 days \pm 7-day window) after the first response. After 1 year on study treatment, the frequency of disease response assessments will be reduced to every 12 weeks (84 days \pm 7 days).
Subjects who discontinue study treatment for reasons other than consent withdrawal or radiologically-confirmed disease progression by RECIST Version 1.1 will continue to receive imaging scans every 8 weeks (56 days \pm 7 days) until subject has radiologically-confirmed disease progression, initiates a new anticancer therapy, dies, withdraws consent, is lost to follow-up, or the study closes, whichever comes first. Tumor imaging may also be performed whenever disease progression is suspected.
12. See [Appendix 12.7 Laboratory Assessments]. Clinical laboratory tests will be performed locally prior to dosing. If tests were performed within 7 days prior to the first day of dosing, they do not need to be repeated on cycle 1 day 1.

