13. Clinical laboratory tests at screening and on cycle 1 day 8 are to be performed after the subject has been fasting in order to ensure accurate interpretation of lab values such as glucose values. Fasting status will be recorded in source documents. Fasting is not necessary for laboratory tests performed at all other visits.
14. If HbA1c is elevated (\geq 6.5%), refer subject to appropriate provider during cycle 1 for glucose management.
15. Prior to performing 12-lead ECGs, subjects should rest in supine position (or semi-recumbent, if supine is not tolerated) for 10 minutes. ECGs will be read and assessed locally.
16. Repeated as clinically indicated throughout the study. Include but not limited to: visual acuity, slit lamp, tonometry examination, and dilated fundus examination. EOT slit lamp examinations are only required for subjects who experience ocular AEs during the study and must be performed \geq 4 weeks from last dose.
17. At least 7 days must elapse between doses of enfortumab vedotin. Subjects should be observed during enfortumab vedotin administration and for at least 60 minutes following the infusion for the first 3 cycles.
18. The EOT visit should occur within 7 days of the last dose of enfortumab vedotin or when the decision is made by the investigator to discontinue the subject from treatment, or prior to the initiation of another anticancer therapy, whichever occurs earlier.

Table 2 **Schedule of Assessments – Cohort 9**

Assessments	Period		Screening/Baseline		Treatment						Follow-up			
					Cycles 1 and 2				Subsequent Every Cycle	Every 6 Weeks ¹¹	EOT	30-day Safety Follow-up	Post Treatment Follow-up	Long-Term Follow-up
Cycle Day			-28 to -1	-7 to -1	1	8	15	1	8		Date of last dose ₂₁	30 days from last dose	Every 9 weeks ₁₂	Every 12 weeks
Visit Window (Days)			0	0	0	± 3	± 3	± 3	-1 to + 4	± 7	+ 7	+ 7	± 7	± 7
General Study Procedures														
Informed Consent			X											
Tumor Tissue Sample ^{1,2}			X											
PD-L1 Test Result ³			X											
Confirmation of Eligibility per Inclusion/Exclusion Criteria			X		X									
Medical History/Disease History/Demographics			X											
Subject Enrollment					X									
PGx Blood Sample (optional)				X										
Pregnancy Test ⁴				X	X			X			X	Pregnancy test monthly until 6 mo after last dose of study treatment		
Physical Examination ⁵				X	X			X			X		X	
Weight				X	X			X			X			
Vital Signs				X	X	X		X	X		X			
ECOG Performance Status				X	X			X	X		X		X	

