7.2.2 Laboratory Assessments

See [Appendix 12.7 Laboratory Assessments] for the list of clinical laboratory tests (including hematology, biochemistry, HbA1c and lipid panel) to be performed and refer to Schedules of Assessments [Table 1] and [Table 2] for timing and frequency. Laboratory tests will be sent to the local laboratory for analysis. Redacted copies of laboratory reports for all local laboratory testing will be submitted electronically by the site to a central vendor for data entry processing. Clinical laboratory tests will be performed locally prior to dosing. Tests will be obtained as indicated in the Schedules of Assessments [Table 1] and [Table 2]. If tests were performed within 7 days prior to the first day of dosing, they do not need to be repeated on cycle 1 day 1. Clinical laboratory tests at screening and on cycle 1 day 8 are to be performed after the subject has been fasting in order to ensure accurate interpretation of

lab test values such as glucose values. Subject will be provided with food after fasting blood samples are obtained. Fasting status will be recorded in source documents. Fasting is not necessary for laboratory tests performed at all other visits. HbA1c will be obtained at screening/baseline and EOT visits. If HbA1c is elevated ($\geq 6.5\%$), refer subject to appropriate provider during cycle 1 for glucose management. Lipid panel, including total cholesterol, high-density lipoprotein cholesterol (HDL-C), low-density lipoprotein cholesterol (LDL-C) and triglyceride tests, will be obtained at screening/baseline only.

Additional assessments may be done to monitor AEs or as required by dose modification requirements. Additional laboratory tests should be performed according to institutional standard of care.

For women of childbearing potential, a serum pregnancy test will be performed at baseline. A urine or serum pregnancy test will then be repeated on day 1 of each cycle prior to study drug administration at EOT and follow-up visits. After EOT, a monthly (± 7 days) pregnancy test will be maintained until 6 months after the last dose of study treatment.

The investigator or subinvestigator must review the laboratory report and document this review. Clinical significance of out-of-range laboratory findings is to be determined and documented by the investigator or subinvestigator who is a qualified physician.

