12.7 Laboratory Assessments

Laboratory tests will be performed according to the schedules of assessments and sent to the local laboratory for analysis.

Table 14 Clinical Laboratory Tests

Panel/Assessments	Parameters to be Analyzed
Hematology	Hematocrit (Hct) Hemoglobin (Hb) Platelets Red blood cell count (RBC) White blood cell count (WBC) White blood cell count differential (Neutrophils, Eosinophils, Basophils, Lymphocytes, Monocytes) Absolute neutrophil count (ANC)
Biochemistry	Albumin (Alb) Alanine aminotransferase (ALT) Alkaline phosphatase (ALP) Aspartate aminotransferase (AST) Bicarbonate (HCO ₃) Bilirubin (total and direct) Blood urea nitrogen (BUN) Calcium Corrected (CCa) Chloride (Cl) Creatinine Glucose Hemoglobin A1c (HbA1c, screening and EOT only) Lactate dehydrogenase (LDH) Magnesium (Mg) Phosphate (P) Potassium (K) Sodium (Na) Total protein (TP) Uric Acid Lipid panel (screening only), including: Total cholesterol (T chol) High-density lipoprotein cholesterol (HDL-C) Low-density lipoprotein cholesterol (LDL-C) Triglycerides (Trig)
Thyroid Function Tests	Triiodothyronine (T3) or Free Triiodothyronine (FT3) Free thyroxine (FT4) Thyroid stimulating hormone (TSH)
Coagulation (Cohort 9 only)	INR PT PTT
Pregnancy Test	Serum or urine β -human Chorionic Gonadotropin (hCG). See Schedules of Assessments for women of childbearing potential.
Note: Fasting blood samples are required at screening and on cycle 1 day 8 only.	

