6.2.3 Demographic and Other Baseline Characteristics

Demographic and other baseline characteristics will be summarized descriptively by cohort and overall for FAS and RES.

Demographic characteristics:

- Age, Age categories (< 65 years, ≥ 65 to < 75 years, ≥ 75 years), EudraCT age categories (≥ 18 to ≤ 64 years, ≥ 65 to ≤ 84 years, ≥ 85 years)
- Sex
- Ethnicity
- Race
- Region (North America, Asia)
- Baseline Height
- Baseline weight, baseline weight groups (≤ 100 kg, > 100 kg)
- Baseline BMI, baseline BMI categories (< 18.5, ≥ 18.5 to < 25, ≥ 25 to < 30, ≥ 30)

Baseline characteristics:

- Baseline measurable disease (Yes, No)
- Nectin-4 IHC H-score (including 25th percentile and 75th percentile)
- Baseline PD-L1 IHC status (PD-L1 low, PD-L1 high as defined in Table 2)
- ECOG PS (0, 1, > 1)
- Hemoglobin, Hemoglobin categories (< 10 g/dL, ≥ 10 g/dL)
- Albumin, Albumin categories (< LLN, ≥ LLN)
- HbA1C, HbA1C categories (≤ 5.6%, 5.7 to < 6.5%, ≥ 6.5%)
- Fasting glucose, fasting glucose CTCAE grade
- Total cholesterol, total cholesterol categories (low, normal, high)
- Baseline hepatic function group

Baseline hepatic function group is defined per the NCI-ODWG criteria based on total bilirubin and AST at the baseline as follows:

Normal:	total bilirubin ≤ ULN and AST ≤ ULN
Mild dysfunction:	(ULN < total bilirubin ≤ 1.5×ULN) or (AST > ULN and total bilirubin ≤ ULN)
Moderate dysfunction:	1.5×ULN < total bilirubin ≤ 3×ULN
Severe dysfunction:	total bilirubin > 3×ULN

- Baseline renal function group

Baseline renal function group is defined based on estimated creatinine clearance (CrCl) by Cockcroft-Gault formula.

Normal:	≥ 90 mL/min
---------	-------------

Mild insufficiency: ≥ 60 to < 90 mL/min

Moderate insufficiency: ≥ 30 to < 60 mL/min

Severe insufficiency: ≥ 15 to < 30 mL/min

End stage renal disease: < 15 mL/min

Cockcroft-Gault formula for estimating CrCl (mL/min):

$$\frac{[140 - \text{age}(\text{years})] \times \text{body weight (kg)} \times (0.85 \text{ if female})}{\text{serum creatinine (mg/dL)} \times 72}$$

- Baseline tobacco use
 - Prior tobacco history (never used, former smoker, current smoker, unknown)
 - Number of pack-years for current or former smoker
- History of diabetes/hyperglycemia defined as any hyperglycemia SSQ/CMQ

Disease specific history will be summarized descriptively by cohort and overall for FAS and RES.

- Time (months) since initial diagnosis of primary cancer

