6.5.2 Clinical Laboratory Evaluation

The baseline value will be the last nonmissing value taken on or prior to first dose of study drug.

Quantitative values evaluated by local laboratories including hematology, biochemistry, and urinalysis will be summarized using mean, standard deviation, minimum, maximum and median by cohort and overall at each analysis visit. Additionally, a within-subject change will be calculated as the postbaseline measurement minus the baseline measurement and summarized in the same way. Plots of median, 25th percentile, and 75th percentile lab values at each scheduled assessment time will be provided for each laboratory parameter by cohort and overall.

Laboratory results will be graded using NCI-CTCAE, where possible. Parameters that have criteria available for both low and high values, i.e., hypo- and hyper-, will be summarized for both criteria. The same subject can be counted for both values if the subject has different

laboratory values meeting each criterion. NCI-CTCAE grade of laboratory evaluations will be summarized by number and percentage of subjects for each visit. Shift tables of NCI-CTCAE grade change from baseline to worst postbaseline grade for selected laboratory parameters will also be presented. The number and percentage of subjects with treatment-emergent NCI-CTCAE grade 3 or 4 laboratory results will be summarized by cohort and overall. Treatment-emergent NCI-CTCAE grade 3 or 4 laboratory results are defined as: subject's worst postbaseline NCI-CTCAE grade for a laboratory parameter being grade 3 or 4, and the worst postbaseline grade is higher than subject's baseline grade for that laboratory parameter. If baseline grade is missing, any postbaseline grade 3 or 4 laboratory result is considered as treatment-emergent. When determining the worst postbaseline value for a subject, both scheduled and unscheduled lab results collected within 30 days after the last dose of study drug will be included.

Laboratory data will be displayed in listings.

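### SAP 6.5.2 sets the glucose baseline without regard to fasting and summarises change at every visit, so mean glucose change can mix fasting states

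*SAP*

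**What the plan says.** **Protocol, fasting.** Section 1.3 (Table 1 footnote 13, with the same rule in Table 2 footnote 14) states: "Clinical laboratory tests at screening and on cycle 1 day 8 are to be performed after the subject has been fasting". The stated reason is correct interpretation of values such as glucose. Section 7.2.2 adds: "Fasting is not necessary for laboratory tests performed at all other visits". The note to Table 14 in section 12.7 agrees: "Fasting blood samples are required at screening and on cycle 1 day 8 only". On where the information is kept, section 1.3 says: "Fasting status will be recorded in source documents".

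**Protocol, day 1 sample.** Biochemistry is scheduled in days -7 to -1 and again on cycle 1 day 1. If tests were done within 7 days before first dosing, "they do not need to be repeated on cycle 1 day 1".

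**SAP, analysis.** Section 6.5.2 sets one baseline rule for all laboratory tests: "The baseline value will be the last nonmissing value taken on or prior to first dose of study drug". At each visit the value is summarised and "a within-subject change will be calculated as the postbaseline measurement minus the baseline measurement and summarized in the same way". CTCAE grade is tabulated by visit. Grade shift runs from baseline to the worst post-baseline grade, for selected parameters.

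**SAP, baseline table.** Section 6.2.3 lists: "Fasting glucose, fasting glucose CTCAE grade". Fasting glucose is not named elsewhere in the SAP.

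**The concern.** The protocol treats fasting state as necessary to interpret glucose, and the SAP names fasting glucose as a variable at baseline. After baseline the distinction disappears. A difference between a fasting and a non-fasting sample then enters the change from baseline and cannot be told apart from a drug effect. The study is non-randomized (SAP 2.3) and has no control arm in which such an artefact would show.

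The protocol (section 2.2.2) lists hyperglycemia among the three important identified risks of enfortumab vedotin, and laboratory tests are a secondary safety endpoint. A reader of the glucose change table could see a rise that reflects meals. At cycle 1 day 8, the one scheduled fasting visit after baseline, the change could be too low if the baseline was not fasting.

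**Working it through.** The plan states no figure for this point, so there is none to reproduce. The check has four steps.

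**1. How many post-baseline draws must be fasting.** The inputs are the biochemistry rows of Protocol Tables 1 and 2. For a subject with K cycles plus the end-of-treatment visit:

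- Cohorts 1 to 8: cycle 1 days 8 and 15 (2), day 1 of cycles 2 to K (K - 1), end of treatment (1). Total K + 2.
- Cohort 9: cycle 1 days 8 and 15 (2), cycle 2 days 1, 8 and 15 (3), days 1 and 8 of cycles 3 to K (2(K - 2)), end of treatment (1). Total 2K + 2.

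One draw, cycle 1 day 8, must be fasting in each case.

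| K | Cohorts 1 to 8 | Cohort 9 |
|---|---|---|
| 2 | 1 of 4 (25.0%) | 1 of 6 (16.7%) |
| 6 | 1 of 8 (12.5%) | 1 of 14 (7.1%) |
| 12 | 1 of 14 (7.1%) | 1 of 26 (3.8%) |

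**2. Which sample becomes the baseline.** If the day 1 draw is waived, the last pre-dose value is the screening sample, which should be fasting. If a day 1 sample is drawn, it is the last value and carries no fasting requirement. The rule in SAP 6.5.2 accepts either, so baselines can differ in fasting state between subjects. The visit-window rule in SAP 6.9.1 does not refer to fasting.

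**3. What this does to mean change when the drug has no effect.** Let f be the share of subjects with a fasting baseline, g the share of samples at a visit that are in fact non-fasting, and d the mean non-fasting minus fasting glucose difference, taken as the same at baseline and later. Then

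artificial mean change = [g - (1 - f)] × d.

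At cycle 1 day 8, if subjects comply, g = 0 and this is -(1 - f) × d. At a visit where every sample is non-fasting, g = 1 and it is f × d. The documents give none of f, g and d. For illustration only, assume d = 10 to 40 mg/dL:

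| f | Other visits, g = 1 | Cycle 1 day 8, g = 0 |
|---|---|---|
| 1 | +10 to +40 | 0 |
| 0.5 | +5 to +20 | -5 to -20 |
| 0 | 0 | -10 to -40 |

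Taking g = 1 is the extreme case. With f = 1 and g = 0.5 the change at other visits is 0.5 × d, or +5 to +20 mg/dL. With f = g = 0.5 it is zero. The sign and size thus depend on quantities that the plan does not fix.

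**4. Which outputs are touched.** Glucose change by visit is affected directly. Laboratory grade by visit pools fasting and non-fasting samples, mainly at the lower grades. Protocol 6.6.1.3 equates grade 3 or higher with glucose above 250 mg/dL and grade 4 with glucose above 500 mg/dL, with no fasting condition. Hyperglycemia as an adverse event of special interest comes from reported terms (SAP 5.4 and 6.5.1). HbA1c is a listed biochemistry parameter collected at screening and end of treatment, so its change is already planned.

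**The case against.** Much of the case on the other side stands.

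- **Grade shift.** A reader might infer that grade shift is computed at every visit. It is not. Grade is tabulated by visit, the shift is baseline to worst for selected parameters, and the SAP does not say that glucose is one of them.
- **Hyperglycemia as a whole.** A reader might infer that this risk is measured only through mixed samples. The special-interest tables cover grade, relatedness, seriousness, discontinuation, reduction and interruption, and treatment-emergent grade 3 or 4 laboratory results are counted as well. One limit is that Protocol 12.4.1.1 makes an abnormal result an adverse event only when the investigator judges it clinically significant, so these tables do not replace the laboratory summary.
- **Meal effect.** That fasting is not required at a visit does not mean that every sample there followed a meal.
- **Day 1 baseline.** Screening biochemistry falls in days -7 to -1, so a subject on schedule qualifies for the waiver and the day 1 draw is optional. The pre-dose glucose check in Protocol 6.6.1.3 is not stated to enter the laboratory dataset.
- **A hidden early rise.** Observed values, medians with quartiles, grades by visit and listings are all planned, so the fasting cycle 1 day 8 values are shown whichever baseline is used. Only the change is distorted.
- **The baseline row.** Its label may mean that a fasting value will be selected, and derivation detail may sit in specifications outside these documents. The SAP itself does not settle this.

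None of this supplies the missing rule. Applied as written, SAP 6.5.2 subtracts a baseline of either fasting state from every later value.

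**Conclusion.** The point holds as a gap in the laboratory analysis of glucose. Following SAP 6.5.2 as written, mean change and the lower laboratory grades by visit can mix fasting states, with 1 of 8 scheduled post-baseline draws fasting in cohorts 1 to 8 and 1 of 14 in cohort 9 (six cycles plus end of treatment). The cycle 1 day 8 change and the fasting glucose row in SAP 6.2.3 are at risk only for subjects whose last pre-dose sample was a non-fasting day 1 draw.

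The counts follow from the schedules. The size of the bias does not: 10 to 40 mg/dL is an assumption, and the shares f and g are unknown. The documents do not support a claim that glucose change is wrong by a given amount or in a given direction. They also do not reproduce the criteria for grades 1 and 2, so nothing here relies on whether those require fasting.

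The consequence is limited to descriptive safety reporting. The primary endpoint, error rates and sample size are unaffected, and no stated decision rule uses mean glucose change. The change is still worth making, because the single-arm design leaves within-subject change as the main reference and the remedy is cheap.

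**What to change.** In SAP 6.5.2 and 6.2.3:

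1. Define the glucose baseline as the last fasting pre-dose sample, scheduled at screening, and use it for the fasting glucose row.
2. Report cycle 1 day 8 as the fasting-to-fasting change.
3. Keep observed values and changes at the other visits, labelled separately as visits where fasting was not required. Dropping those changes would depart from Protocol 9.5.2, which plans change from baseline at each visit.
4. State whether actual fasting status is in the analysis data or whether only the scheduled visit is used.

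No new table is needed for HbA1c change or for grade 3 or 4 glucose, since both are already planned.

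The cost is SAP wording and one extra table or footnote. The limitation is that fasting status is recorded in source documents. If it was not also captured in the database, the visit label shows scheduled fasting, which may differ from actual fasting, and the table should say so. The change concerns tabulation only and proposes no clinical rule.

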6.5.2.1 Liver Safety Assessment

The liver safety assessments will be summarized by the categories below based on the measurements from Alkaline Phosphatase (ALP), Alanine Transaminase (ALT), total bilirubin, Aspartate Transaminase (AST) and their combination. These parameters will be based on measurements from local laboratories. The normal ranges from the corresponding laboratories should be used.

The subject's highest value postbaseline (including unscheduled visits) will be used.

- $ALT > 3 \times ULN, > 5 \times ULN, > 10 \times ULN, > 20 \times ULN$
- $AST > 3 \times ULN, > 5 \times ULN, > 10 \times ULN, > 20 \times ULN$
- $ALT \text{ or } AST > 3 \times ULN, > 5 \times ULN, > 10 \times ULN, > 20 \times ULN$
- $ALP > 1.5 \times ULN$
- $Total \text{ Bilirubin} > 2 \times ULN$
- $(ALT \text{ or } AST > 3 \times ULN) \text{ and } Total \text{ Bilirubin} > 2 \times ULN *$
- $(ALT \text{ or } AST > 3 \times ULN) \text{ and } ALP < 2 \times ULN \text{ and } Total \text{ Bilirubin} > 2 \times ULN *$

* Combination of values measured within the same day or up to 1 day apart

The denominator for each criterion will be the number of subjects who have at least one value postbaseline. The number and percentage of subjects meeting the criteria will be summarized by cohort and overall.

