5.1 Inclusion Criteria

Subject is eligible for participation in the study if all of the following apply:

1. Institutional Review Board (IRB)/Independent Ethics Committee (IEC) approved written informed consent and privacy language as per national regulations (e.g., Health Insurance Portability and Accountability Act Authorization for US study sites) must be obtained from the subject prior to any study-related procedures (including withdrawal of prohibited medication, if applicable).
2. Subject is considered an adult according to local regulation at the time of signing the informed consent form (ICF).
3. Subject has measurable disease by RECIST Version 1.1.
4. Subject has accessible archival tumor tissue from either the primary tumor or a metastatic site, for which source and availability have been confirmed prior to study treatment. If no archival tumor tissue is available, the subject will have a biopsy to obtain tumor tissue prior to study treatment. If the subject is unable to undergo a biopsy due to safety concerns, enrollment into the study must be discussed with the medical monitor.
 - a. For cohort 9 only: Subject should submit archival or fresh tumor tissue sample for PD-L1 central testing during screening if no local PD-L1 test result is available. Central test result for PD-L1 will be required prior to subject enrollment. For cohort 9 subjects with local PD-L1 test result confirming CPS ≥ 1 , archival or

fresh tissue sample for exploratory analysis should be submitted within 5 days of enrollment.

5. Subject has ECOG performance status of 0 or 1.
6. Subject has the following baseline laboratory data. If a subject has received a recent blood transfusion, the hematology tests must be obtained ≥ 28 days after any blood transfusion.
 - absolute neutrophil count (ANC) $\geq 1.0 \times 10^9/L$
 - platelet count $\geq 100 \times 10^9/L$
 - hemoglobin ≥ 9 g/dL
 - serum total bilirubin $\leq 1.5 \times$ upper limit of normal (ULN) or $\leq 3 \times$ ULN for subjects with Gilbert's disease
 - creatinine clearance (CrCl) ≥ 30 mL/min as estimated per institutional standards or as measured by 24-hour urine collection (glomerular filtration rate [GFR] can also be used instead of CrCl).
 - Cohorts 1-8: alanine aminotransferase (ALT) and aspartate aminotransferase (AST) $\leq 3 \times$ ULN
 - Cohort 9: ALT and AST $\leq 2.5 \times$ ULN ($\leq 5 \times$ ULN for subjects with liver metastases)

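### The liver-safety table in SAP 6.5.2.1 takes no account of baseline, so its ALP row, and in narrow groups its bilirubin and ALT/AST > 3 x ULN rows, mix pre-existing with new elevations

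*SAP*

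**What the plan says.** SAP 6.5.2.1 lists liver criteria for ALT, AST, ALT or AST, ALP, total bilirubin and two combinations, all as fixed multiples of the local laboratory's ULN. The subject's "highest value postbaseline (including unscheduled visits) will be used". On who is counted: "The denominator for each criterion will be the number of subjects who have at least one value postbaseline". The section sets no baseline condition, shift or baseline category. Protocol Appendix 12.5 leaves the end-of-study liver enzyme analysis to the SAP.

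The entry limits are in Protocol 5.1, criterion 6, which opens "Subject has the following baseline laboratory data". It covers neutrophils, platelets, hemoglobin, total bilirubin, creatinine clearance, ALT and AST. ALP is absent, and no exclusion criterion names it. Bilirubin is capped at 1.5 x ULN, with a 3 x "ULN for subjects with Gilbert's disease". ALT and AST are capped at 3 x ULN in cohorts 1 to 8. In cohort 9 the cap is 2.5 x ULN, with a 5 x "ULN for subjects with liver metastases".

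SAP 6.5.2, the parent section, does plan outputs that use baseline:
- By visit: "NCI-CTCAE grade of laboratory evaluations will be summarized by number and percentage of subjects for each visit".
- Shift: "Shift tables of NCI-CTCAE grade change from baseline to worst postbaseline grade for selected laboratory parameters will also be presented". The selected parameters are not named.
- Within-subject change from baseline, summarized by visit.
- A treatment-emergent table requiring the worst grade to exceed the baseline grade, for worst grade 3 or 4 only.
- Listings: "Laboratory data will be displayed in listings".

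SAP 6.2.3 also summarizes a baseline hepatic function group built from bilirubin and AST.

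**The concern.** A subject who enters above one of these limits and does not change is counted in that row exactly like a subject whose value rose on treatment. The study is open-label and non-randomized with no control arm (SAP 2.3), so the subject's own baseline is the only internal reference for such a row. Without it, a reader of the table cannot tell a new ALP elevation from one present at entry, and the same holds for bilirubin and ALT/AST in the two exception groups. The separation then has to be made from the listings, subject by subject. At stake is how one descriptive safety table is read.

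**Working it through.** **1. Table limits against entry limits.**

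| Criterion in SAP 6.5.2.1 | Rows | Entry limit (Protocol 5.1, criterion 6) | Can be met at entry? |
|---|---|---|---|
| ALP > 1.5 x ULN | 1 | none | yes, any cohort |
| Bilirubin > 2 x ULN | 1 | 1.5 x ULN; 3 x ULN in Gilbert's | Gilbert's only |
| ALT, AST, ALT or AST > 3 x ULN | 3 | cohorts 1–8: 3 x ULN; cohort 9: 2.5 x ULN, 5 x ULN with liver metastases | cohort 9 with liver metastases only |
| The same three at > 5, > 10, > 20 x ULN | 9 | as above | no |
| Two ALT/AST-with-bilirubin combinations | 2 | both sets | only a cohort 9 subject with both exceptions |

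Total: 1 + 1 + 3 + 9 + 2 = 16 rows. Open at entry: 1 + 1 = 2 in cohorts 1 to 8 and 1 + 1 + 3 = 5 in cohort 9.

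**2. Weight of one unchanged subject.** In a 40-subject cohort it is 1/40 = 2.5 points. In the overall column, at the protocol's approximate total of 320, it is 1/320 = 0.31 points.

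**3. Direction of the effect.** Let N be the subjects, B those above a limit at baseline, C those of the B who are above it again afterwards, and W those newly above. The table shows M = C + W out of N. The new-onset percentage is W/(N − B).

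- Counts: M = C + W, so M is never below W.
- Percentages: M/N = (B/N)(C/B) + ((N − B)/N)(W/(N − B)). This is a weighted average of the persistence proportion C/B and the new-onset proportion. The table percentage is too high when C/B exceeds the new-onset proportion and too low when C/B is smaller.

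**4. Why separate baseline and post-baseline counts do not settle it.** Without linkage, W lies between max(0, M − B) and min(M, N − B). With assumed figures N = 40, B = 3, M = 5:

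- Lower end: max(0, 5 − 3) = 2, so 2/37 = 5.4%. All three baseline elevations persist.
- Upper end: min(5, 37) = 5, so 5/37 = 13.5%. None of the three is above the limit at any later visit.
- The table shows 5/40 = 12.5% in both cases.

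**5. Scale under assumed prevalence.** Take the ALP row, assume that baseline elevations persist, and let b be the baseline prevalence and q = 10% the new-onset rate. The table shows b + (1 − b)q, and the pre-existing share of those counted is b divided by that total.

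| Assumed b | Expected pre-existing among 40 | Table shows | Pre-existing share |
|---|---|---|---|
| 5% | 2 | 14.5% | 34% |
| 10% | 4 | 19.0% | 53% |
| 20% | 8 | 28.0% | 71% |

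Neither b nor q is in the documents.

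**6. What the other outputs add.** Protocol Table 9, footnote a, puts grade 2 at > 3 to 5 x ULN for ALT/AST and > 1.5 to 3 x ULN for bilirubin when baseline is normal. If baseline is one of the tabulated visits and grades are read against ULN, the by-visit table gives the number above ALT/AST > 3 x ULN at entry and an upper bound for bilirubin > 2 x ULN. The moderate class of the baseline hepatic function group (bilirubin > 1.5 to 3 x ULN) also gives that upper bound among eligible subjects. The grade 3 or 4 table does link baseline to worst value, but misses a worst value in the grade 2 ranges, where the 2 x ULN bilirubin limit falls. For ALP, SAP 5.4 says it is graded, but the documents do not give the grade limits, so whether any grade matches 1.5 x ULN cannot be checked here.

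**The case against.** The strongest reply is that this is a transparent maximum-value screen. It states what it counts, is not labelled treatment-emergent or drug-related, and contradicts nothing in the protocol. Nine of the 16 rows cannot be met at entry, and two more need one cohort 9 subject with both exceptions. Pre-existing abnormality is also handled elsewhere. Under SAP 5.4 an event present before treatment is treatment-emergent only if it worsens. Protocol Appendix 12.5 requires a case-by-case work-up of confirmed moderate or severe liver abnormalities, with a higher moderate ALT/AST limit for subjects with liver metastases. Table layouts are left to separate specifications (SAP 6.1) that are not available here.

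Most of this stands, and it sets the priority. It does not close the gap. Within-subject change is summarized by visit, not at the subject's maximum. The shift tables may or may not include liver tests. The hepatic function group uses neither ALP nor ALT and is not crossed with this table. None of the outputs is committed to linking a subject's baseline to that subject's maximum at these limits.

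Two stronger readings are tempting. A reader might infer that the affected percentages are always inflated. Step 3 shows that this is true of counts only: in the example the new-onset figure can be 13.5% against 12.5% shown. A reader might also infer that the plan ignores baseline liver status. It does not; the information is partly tabulated and available in the listings.

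**Conclusion.** The point holds as a minor one. SAP 6.5.2.1 mixes pre-existing with new elevations in the ALP row for every cohort, in the bilirubin row for subjects with Gilbert's disease, and in the three ALT/AST > 3 x ULN rows for cohort 9 subjects with liver metastases. The main exposure is ALP.

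The size is unknown. It depends on baseline prevalence and persistence, neither of which the documents give, and the figures in steps 4 and 5 are illustrations. The row comparison assumes that subjects meet the entry criteria and that the eligibility value stands as the baseline value.

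The documents would not support a claim that this threatens the trial's conclusions. The table is descriptive, no stopping or efficacy rule uses it, and adverse events are summarized separately.

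**What to change.** Keep the existing counts and add to SAP 6.5.2.1:

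*Each single-parameter criterion (and ALT or AST) will also be summarized among subjects who did not meet it at baseline (baseline as defined in Section 6.5.2); subjects with a missing baseline value will be shown separately. For the two combined criteria, the baseline values of any subject meeting them will be displayed.*

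Missing baselines are kept apart because an elevation of unknown origin should not be called new. The SAP also has no single rule to borrow: 6.5.2 treats a missing baseline grade as treatment-emergent for grade 3 or 4 results, while 6.9.2 drops missing baselines from change-from-baseline analyses. The combined criteria get a display because 6.5.2.1 pairs values on the same day or one day apart, whereas baseline is the last nonmissing value for each test, so meeting the pair at baseline is not defined.

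The cost is two sentences of SAP text and a slightly longer table. ALT, AST, ALP and bilirubin are already collected at screening, and the baseline value is already defined, so no new data are needed.
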